data). The inclusion of all follow-up time points in the model as well as covariates identified to be associated with withdrawal will assist in meeting this assumption and minimizing the risk of bias. Although the assumption for missing data is weaker under the likelihood based analysis compared to complete case analysis, a non-ignorable missing data mechanism is possible. Sensitivity analysis using selection and pattern mixture models will be employed to evaluate the robustness of conclusions to the missing at random (MAR) assumption.

Analysis Plan for Year 2 Outcomes

Year 2 outcomes for SF-36 and other continuous outcomes will be analyzed using linear mixed effects models (lme) that include both first and second year outcomes. The outcomes will be change from baseline. The purpose of the lme is to address missing second year outcomes. Since the year 2 assessments were missing mainly for logistical reasons (at 2 sites, research staff neglected to follow up with participants during specific time intervals), the missing at random (MAR) assumption of the lme is valid. The model will include treatment group, time period, and group*time interaction. To address within-subject correlation, patient id will be a random effect. There will be no adjustment for surgeon, since some surgeons had few patients, and no adjustment for baseline variables, since these were similar between groups. The treatment effect at year 2 will be tested using model contrasts. The year 1 treatment effect will be tested similarly, to confirm previous analyses obtained by t-test and anova. The models will be used to compare the 2 randomized groups and the “as treated groups.” We will not address multiple comparisons for the “as treated” analyses because they are considered to be exploratory.

Analysis Plan for Return to Work

The return to work analysis will include all time periods up to 12 months (1, 3, 6, and 12 months). Groups will be compared via Kaplan-Meier plots and log-rank tests. To address multiple comparisons when comparing the as-treated groups pairwise comparisons will be performed at $p=0.025$ to account for 2 comparisons (DL vs DF and DL vs VF).

Analysis Plan for Cost-Effectiveness

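### The Year 2 mixed model analyses change scores without the baseline score as a covariate; similar baseline means do not justify that, and the cost is precision

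*Combined protocol and SAP*

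**What the plan says.** The subsection on Year 2 outcomes in section II.G.c sets a linear mixed model for SF-36 and the other continuous outcomes, using Year 1 and Year 2 together. On the outcome scale: "The outcomes will be change from baseline". On the fixed effects: "The model will include treatment group, time period, and group*time interaction". Patient is the only random effect. Two omissions are explained. For the baseline score the plan sets "no adjustment for baseline variables, since these were similar between groups". For surgeon its wording is: "There will be no adjustment for surgeon, since some surgeons had few patients". The model compares the randomised groups and the as-treated groups. It also re-tests the Year 1 effect, as confirmation of earlier t-test and analysis-of-variance results.

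The cause given for most of the missing Year 2 data is that "at 2 sites, research staff neglected to follow up with participants during specific time intervals". From this the plan concludes that "the missing at random (MAR) assumption of the lme is valid". No site term is listed.

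The primary one-year model, earlier in II.G.c, adjusts for baseline SF-36 PCS and takes surgeon as a random effect. For that analysis the plan adds: "Sensitivity analysis using selection and pattern mixture models will be employed". The Year 2 text does not say whether this carries over. Section III.A stratifies randomisation by site.

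**The concern.** Subtracting the baseline is not the same as adjusting for it. A change score fixes the slope of follow-up on baseline at 1, whereas the pilot data put it near 0.7. The excess slope adds noise to each patient's value even when the two arms have identical baseline means. In that case the two analyses give the same point estimate, but the unadjusted one reports the wider standard error. Observed similarity therefore does not address what is lost.

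Where the arms do differ a little by chance, the change score over-corrects and carries part of the difference into the estimate. The plan says the groups were similar without saying how similar.

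The same model is also used for the Year 1 contrast, so SF-36 PCS at one year would be tested with baseline adjustment in the primary analysis and without it here.

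Site is a secondary matter. It is the randomisation stratum and the stated main source of missing Year 2 data, yet the model does not condition on it. The reason given for dropping surgeon is not stated to cover site.

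**Working it through.** **Inputs from section II.G.d.** Pilot SF-36 PCS, given as pre-op SD, post-op SD, correlation and printed change SD:
- all patients: 10.9, 11.8, 0.64, 9.7
- ventral (n = 45): 10.3, 11.7, 0.64, 8.2
- dorsal (n = 70): 11.3, 11.6, 0.66, 9.5

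Expected analysable patients are 55 ventral and 82 dorsal. The target is 5 points, two-sided 5%.

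**Formulas.** Var(change) = s0² + s1² − 2ρ·s0·s1. Var(adjusted) = s1²(1 − ρ²).

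**Reproducing the plan's figure.** All patients: 118.81 + 139.24 − 2(0.64)(10.9)(11.8) = 93.42, so the SD is 9.67 against the printed 9.7. The dorsal row gives 9.45 against 9.5. The ventral row gives 9.42 against 8.2; the printed 8.2 would need a correlation of 0.73 instead of 0.64.

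**Year 1, complete data.**
- All patients: 93.42 / 82.21 = 1.14.
- Dorsal: 89.22 / 75.95 = 1.17.
- Ventral: 88.73 / 80.82 = 1.10, or 1.05 if its printed change SD is right.
- Standard error: 1/55 + 1/82 = 0.03038, so √(93.42 × 0.03038) = 1.68 and √(82.21 × 0.03038) = 1.58.
- Power for 5 points (noncentral t): 83.8% against 88.1%.

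The all-patients row mixes the arms and so contains the treatment difference. Pooling within arms gives (44 × 88.73 + 69 × 89.22)/113 = 89.0 and (44 × 80.82 + 69 × 75.95)/113 = 77.8. The ratio is again 1.14, and power is 85.5% against 89.8%.

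**Chance baseline difference.** The slope is 0.64 × 11.8/10.9 = 0.693, so each point of baseline difference moves the change-score contrast by 1 − 0.693 = 0.31 points. The baseline difference has standard error 10.9 × √0.03038 = 1.90. A difference of that size moves the Year 1 contrast by 0.58 points.

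**Year 2.** The documents give no Year 2 correlations, numbers or target, so the following is assumed: SDs 10.9, 11.8, 11.8; baseline–Year 1 correlation 0.64; baseline–Year 2 correlation 0.60–0.70; Year 1–Year 2 correlation 0.60–0.80; missing fraction m of 10–40%; and the same 55/82 and 5 points as a yardstick. The variance is proportional to V₂[(1 − r²)/(1 − m) + r²]. V₂ is the Year 2 variance and r the Year 1–Year 2 correlation, each taken for the change score or for the residual given baseline.

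Reference case (0.65, 0.70, m = 20%):
- Change: V₂ = 90.84, r = 0.547, giving 106.8.
- Adjusted: V₂ = 80.41, r = 0.486, giving 95.8.
- Ratio 1.11; power 78.7% against 82.9%.

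| Baseline–Year 2 correlation | Variance ratio | Power gain (percentage points) |
|---|---|---|
| 0.60 | 1.13–1.16 | 5.2–5.8 |
| 0.65 | 1.10–1.12 | 4.0–4.4 |
| 0.70 | 1.07–1.09 | 2.6–3.1 |

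A ratio of 1.07–1.16 is like discarding about 7–14% of patients (1 − 1/ratio).

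**Site (all inputs assumed).** A mean shift at the two sites, constant or changing over time, leaves bias of 0 in the randomised contrast because the arms have equal shares there. In an as-treated contrast the bias is the shift times the difference in shares: 4 points × 30 percentage points = 1.2 at Year 1. Missing data reduce it to 0.81–1.05 at Year 2.

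**The case against.** The unadjusted change-score contrast is unbiased on average under randomisation. It matches the endpoint definition in II.G.b and suits a model meant partly to confirm earlier unadjusted tests. Year 2 is neither the primary nor a listed secondary endpoint. The Year 2 text is in the past tense, so adding a covariate now is a change made with data in hand. No baseline imbalance is reported, so the 0.58-point shift is an illustration. Absolute power depends on the pilot row used: with the printed change SDs pooled within arms, change-score power alone is about 88.5%. All of this stands, and it limits the stakes. It does not make similarity a reason to omit the covariate, and the 14% excess variance is nearly the same on the all-patients and within-arm figures.

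A reader might infer that leaving site out biases the randomised Year 2 contrast, or that missing at random is false. The documents support neither. Missingness driven by site lapses is compatible with missing at random, and a site mean shift alone does not bias the randomised contrast. If the treatment effect itself differed at the two sites (assumed 5 elsewhere, 2 there, 20% of patients), missing data would move the contrast to 4.50–4.61 from 4.40, but site or site-by-time terms would not correct that. The as-treated exposure is ordinary confounding, in analyses left without multiplicity control "because they are considered to be exploratory". The plan also speaks of surgeons and centres almost as one unit in II.G.d, so small clusters may be the unstated reason for omitting site. A random site effect could accommodate them.

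**Conclusion.** The point holds as a loss of precision. For SF-36 PCS the change score carries about 14% more variance than the baseline-adjusted analysis on pilot figures (1.05 to 1.17 across the two approach rows). At Year 1 with 55/82 and complete data this costs about 4 percentage points of power for 5 points. At Year 2 the ratio is about 1.07–1.16 and the cost about 3–6 points, resting on the assumed correlations and missing fractions. If the printed ventral change SD held, the Year 2 ratio would be 1.04–1.12. The documents give no correlations for the other outcomes, so nothing is claimed about their size.

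The importance is moderate: the Year 2 contrast and the repeated Year 1 contrast are affected, while the primary model already adjusts. The site and missing-data part is minor. It concerns confounding in exploratory as-treated comparisons and a statement of validity that should be an assumption. It is not a finding of bias in the randomised comparison.

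**What to change.** In the Year 2 mixed model, add the baseline value of each outcome as a covariate for both the Year 1 and Year 2 contrasts. Allow its slope to differ by visit. Keep the unadjusted model as a sensitivity analysis, and state that the covariate was added after data had been seen.

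As a lesser change, add a site term (random if sites are small), mainly to reduce site confounding in the as-treated comparisons. A site main effect removes that confounding only if the site shift is constant over time, so site-by-time can serve as a check. Describe missing at random as assumed given site and the modelled data. Report a sensitivity analysis without the two affected sites, and say whether the selection and pattern-mixture analyses apply to Year 2.

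The cost is SAP wording and a re-run on data already collected. The downside is small shifts from earlier estimates and, if site is fixed, a few degrees of freedom.

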- 9) Initial Hospital Admission Data Sheet
- 10) 3 Months and 1 Year Radiology
- 11) End of Study
- 12) Adverse Event Form
- 13) Serious Adverse Event Report Form
- 14) Serious Adverse Event Follow-up Report Form
- 15) SF-36 questionnaires (pre-op, 3 months, 6 months, 1, 2, 3, 4, and 5 years),
- 16) Neck Disability Index questionnaires (pre-op, 3 months, 6 months, 1, 2, 3, 4, and 5 years)
- 17) mJOA, (pre-op, 3 months, 6 months, and 1 year)
- 18) EuroQol-5D (pre-op, 3 months, 6 months, 1, 2, 3, 4, and 5 years)
- 19) Health Resource Utilization Diary (1 month, 3 months, 6 months, 1 year)
- 20) Report of Second Cervical Surgery
- 21) Death Form
- 22) Inpatient Hospital and Rehabilitation Utilization Data Sheet
- 23) Long term follow-up phone questionnaire (2, 3, 4, and 5 years)

b. Study endpoints.

Subjects will be followed for 5 years. The primary endpoint will be the 1-year change in SF-36 physical component summary score (PCS) at one year. Secondary endpoints will include the 1-year change in mJOA, NDI, and EuroQol-5D scores as well as the observed complication rates, health service utilization, work status, and sagittal balance measurements.

c. Statistical Methods.

Primary analyses will include all subjects randomized using an intent-to-treat approach. The primary endpoint is the 1-year change in Physical Component Summary of the SF-36 (SF-36 PCS) at one year. A likelihood-based analysis using a mixed model will be used to compare SF-36 PCS between groups. This model will adjust for baseline SF-36 PCS, as well as study surgeon using a random effects model. All time points will be included in the model, and each subject will contribute data for the time points at which they were assessed. The model enables a statistical comparison between treatment groups at each time point, though the comparison at the one-year time point will be the primary analysis. The primary advantage of the mixed model, when compared to commonly used methods such as complete case analysis and single imputation (e.g. last observation carried forward), is its flexibility in handling missing data. This analysis will assume that missing data occurs at random (i.e. the missing data value can be dependent on observed data, but independent of unobserved

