- The ICER will be calculated in a three-way extended dominance analysis, comparing each surgical treatment to the others. If a surgical procedure is both less costly and provides higher QALYs gained, that treatment will be dominant

over the others.

- A comparison of anterior and posterior approaches (namely, grouping the two posterior procedures) will be performed independently from the ICER model.
- Probabilistic analysis will be performed to account for sampling variation around ICER point estimates.
- Cost/QALY gained will be reported for each surgical treatment and for each approach.

d. Power Analysis.

Sample size for Specific Aim #1a (Ventral surgery is associated with superior SF-36 PCS outcome at one year compared to dorsal (fusion or laminoplasty surgery):

Sample size estimates were calculated based on analysis of covariance model with $\alpha = 0.05$ at 80% and 90% power using Power Analysis and Sample Size software (PASS 2008, NCSS, LLC. Kaysville, Utah). The primary endpoint is the SF-36 PCS. This component of the SF-36 is derived from the sums of scores of 21 items and thus exhibits distributional behavior commensurate with assumptions for parametric analysis. Our preliminary data suggest standard deviations for SF-36 PCS between 10 and 12 and correlations of baseline with one year SF-36 PCS between 0.6 and 0.7. *The following table describes the total sample size (2:3 ventral-dorsal randomization) required to detect a five point difference in SF-36 PCS one year post-surgery for various combinations of power, standard deviation and one year correlations under a fixed design.*

A minimum sample size of **137** patients provides at least 90% power (see Tables below):

Surgery (N)	Pre-op	Post-Op	Correlation between Pre- and Post-Op	Difference
Ventral (45)	35.5 ± 10.3	44.2 ± 11.7	0.64	+ 8.7 ± 8.2
Dorsal (70)	35.8 ± 11.3	39.8 ± 11.6	0.66	+ 4.0 ± 9.5
Dorsal Fusion (42)	35.0 ± 11.7	39.6 ± 12.4	0.65	+ 4.6 ± 10.0
Laminoplasty (28)	37.0 ± 10.9	40.1 ± 10.6	0.67	+ 3.1 ± 8.8
All patients (115)	35.7 ± 10.9	41.5 ± 11.8	0.64	+ 5.8 ± 9.7

Difference / SD	Correlation	80% Power / 5% Type I error (2-sided)			90% Power / 5% Type I error (2-sided)		
		N _{Ventral}	N _{Dorsal}	N	N _{Ventral}	N _{Dorsal}	N

5 / SD = 10	0.60	38	56	94	50	74	124
5 / SD = 10	0.65	40	59	99	53	78	131
5 / SD = 10	0.70	42	62	104	55	82	137

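### The year 2 model drops the baseline score, surgeon and the 3- and 6-month visits for reasons that do not support it, and its year 1 contrast adds little confirmation of the earlier t-test and ANOVA

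*Combined protocol and SAP*

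**What the plan says.** Section II.G.c, Statistical Methods, sets the primary analysis: an intent-to-treat mixed model for SF-36 PCS using every time point. "This model will adjust for baseline SF-36 PCS, as well as study surgeon using a random effects model", and "the comparison at the one-year time point will be the primary analysis". On missing data it relies on "The inclusion of all follow-up time points in the model as well as covariates identified to be associated with withdrawal" to help meet the missing-at-random assumption.

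The Analysis Plan for Year 2 Outcomes then specifies a different model, restricted to years 1 and 2. "The outcomes will be change from baseline". "The model will include treatment group, time period, and group*time interaction", with patient as a random effect. There is to be "no adjustment for surgeon, since some surgeons had few patients, and no adjustment for baseline variables, since these were similar between groups". Its stated purpose is to deal with missing year 2 values, which the plan attributes mainly to missed follow-up by staff at two sites. It adds a year 1 use: "The year 1 treatment effect will be tested similarly, to confirm previous analyses obtained by t-test and anova".

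Section II.G.d, Power Analysis, reports "correlations of baseline with one year SF-36 PCS between 0.6 and 0.7" and pilot means and SDs. Section II.G.c plans no t-test or ANOVA for the one-year continuous outcomes. The year 2 plan does not say which outcomes and groups those tests covered, or how they relate to the primary model.

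**The concern.** The year 2 model leaves out three things that the primary model contains, all already collected. Two of the omissions are justified in the text, but the reasons answer a different question. Balance between groups bears on confounding, not on the outcome variance that baseline explains. Sparse surgeons make separate fixed effects hard to estimate; a random effect is the usual remedy. Dropping the 3- and 6-month visits is not explained.

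At stake is a year 2 comparison that is less precise than the data allow and that uses less of the information meant to protect against informative loss. There is also a question of reading. If the year 1 contrast agrees with the earlier t-test and ANOVA, a reader may take that as corroboration, when the model is built so that its estimate will nearly always agree.

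**Working it through.** **1. Precision lost by omitting baseline.** Inputs are from the pilot table in II.G.d (all patients): baseline SD 10.9, one-year SD 11.8, correlation r = 0.64, with a stated range of 0.6-0.7.

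- SD of change = √(10.9² + 11.8² − 2r·10.9·11.8). At r = 0.64: √(118.81 + 139.24 − 164.63) = √93.42 = 9.67. The table gives 9.7, so the plan's own figure is reproduced.
- Residual SD after baseline adjustment = 11.8·√(1 − r²). At r = 0.64: 11.8 × 0.768 = 9.07.

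| r | SD of change | Adjusted SD | Ratio |
|---|---|---|---|
| 0.60 | 10.18 | 9.44 | 0.927 |
| 0.64 | 9.67 | 9.07 | 0.938 |
| 0.70 | 8.83 | 8.43 | 0.954 |

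Simulation gave standard-error ratios of 0.93-0.96, so the standard error is about 4-7% smaller. Baseline balance appears nowhere in these formulas. The documents give no baseline-to-year-2 correlation. If it were 0.50 (assumed, same SDs), the ratio would be 10.22/11.38 = 0.898, so a weaker correlation enlarges the gain over a change score.

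The effect on the pilot estimate is small. The unadjusted difference is 8.7 − 4.0 = 4.7. With slope 0.64 × 11.8/10.9 = 0.69, the adjusted difference is (44.2 − 39.8) − 0.69 × (35.5 − 35.8) = 4.6. In simulated trials the adjusted estimate departed from the t-test estimate with an SD of 0.47-0.68 points.

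**2. Surgeon and visits, side by side.** The primary model already treats surgeon as random, and randomization is stratified by site (III.A), so site is a natural fallback. The year 2 plan places most missing year 2 visits at two sites, which makes site a predictor of missingness, yet the model contains neither site nor surgeon. SF-36, NDI and EuroQol-5D are all collected at 3 and 6 months as well as at years 1 and 2.

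**3. Why the year 1 contrast reproduces the raw difference.** Let c1 and c2 be the changes at years 1 and 2. The likelihood factors as p(c1)·p(c2 | c1). With a full group-by-time interaction, each group's year 2 mean is a free parameter. If everyone with c2 also has c1, the second factor carries no information on the year 1 mean, whose estimate is then the observed group mean of c1. The contrast is the difference in mean change. The same holds for three as-treated groups and an ANOVA.

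Numerical check: 63/96 patients, the SDs above, r 0.60-0.70, 10% missing at year 1, and assumed 20-40% missing at year 2 and year 1-year 2 correlation 0.60-0.85. Across eight settings of 1,000 trials, the largest gap was 2 × 10⁻¹⁴ points. A separate run with 55/82 patients and change SD 9.7 also gave a gap of zero.

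**4. When some patients have year 2 but not year 1.** The gap between the two estimates had an SD of 0.16-0.40 points in the first set of runs (correlation 0.969-0.996). In the second set (5-10% missing at year 1, assumed) the SD was 0.25-0.41, with a largest gap of 0.9-1.6 points. The design difference is 5 points.

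**5. The tests are not identical.** A random-intercept model pools the variance over both years. In the 55/82 runs (year 1-year 2 correlation 0.7, assumed), the two tests fell on opposite sides of 0.05 in about 1-2% of trials with equal SDs, 6% with a year 2 SD of 11.5 (assumed), and 6-9% with year 1 values also missing.

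**6. Shared bias from year 1 loss.** These runs assume about 10% loss (the attrition allowance in II.G.d), a true effect of 5, and correlations of 0.65/0.75/0.85 among follow-up visits. In the first two rows dorsal losses are random.

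| Assumed loss mechanism | Bias, t-test and year 2 model |
|---|---|
| Ventral losses are the lowest 6-month changes | +0.80 / +1.14 / +1.41 |
| Weaker selection, ventral arm only | +0.37 / +0.53 / +0.66 |
| Both arms lose their lowest changes | −0.01 / −0.13 / −0.22 |

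Under the first mechanism, an all-visit likelihood analysis was off by −0.06 / +0.07 / +0.03.

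**The case against.** The year 2 model exists to handle missing year 2 outcomes, and its year 1 contrast is a by-product. Checking that a new model reproduces earlier results is routine, and expected agreement is not a defect. An unadjusted change-score comparison is valid under randomization, and the precision forgone is modest. The plan ascribes the missing year 2 data mainly to logistics and does not expect high withdrawal. For the primary analysis it also plans selection and pattern-mixture sensitivity models.

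Much of this stands. It limits the point to efficiency and interpretation of a secondary analysis. It does not rescue the stated reasons for the omissions, or explain why visits valued in the primary model are set aside here.

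Three stronger readings are tempting, and the documents do not support them:

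- A reader might infer that the year 1 check cannot fail. Exact equality needs everyone seen at year 2 to have been seen at year 1, which the plan does not guarantee. It also needs the earlier tests to have used unadjusted change in the same patients, which is not stated. Even with identical estimates, p-values can differ.
- A reader might infer that the t-test or ANOVA replaced the primary model. No text withdraws that model.
- A reader might infer a bias of 0.8-1.4 points at year 1. That needs one arm to lose its worst patients while the other loses at random, which nothing in the documents suggests.

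**Conclusion.** The point holds as a low-cost improvement to the year 2 analysis. Omitting baseline costs about 4-7% in standard error at the plan's own correlations, assuming that year 2 SDs and correlations resemble those at year 1. The reasons given for omitting baseline and surgeon do not support the choice, and leaving out the 3- and 6-month visits runs against the plan's own missing-data argument.

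Secondarily, the year 1 contrast is a weak check. Its estimate matches a t-test or ANOVA on unadjusted change exactly or to within a few tenths of a point in most simulated trials, so agreement says little about whether the one-year effect is robust. Any bias shared by the two analyses depends on an assumed mechanism and is near zero if both arms lose patients alike. The primary one-year result is unaffected if the model in II.G.c is run as planned.

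**What to change.** For year 2, extend the primary model rather than fitting a separate unadjusted one. Include the baseline value, all visits at which the outcome was collected (3, 6, 12 and 24 months), group by time, and a random surgeon effect, or site as the randomization stratum if surgeon variance cannot be estimated. Read the year 2 contrast from that model. Compare the earlier t-test and ANOVA with the year 1 result of the primary model in II.G.c.

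If the unadjusted model is kept, remove the statement that it confirms the year 1 result, and label its year 1 contrast and the t-test and ANOVA as supportive. In either case, state which outcomes and groups those tests covered and how they relate to the primary model.

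The cost is a few model terms on data already collected and two or three sentences of text. No new patients or visits are needed.

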flexion-extension radiographs will be obtained pre-operatively on all patients and at one year after surgery to assess cervical fusion and/ or radiographic complications. Standing cervical-thoracic-lumbar-sacral films will be obtained on all patients pre-operatively and at one year postoperatively (post-operatively in the randomized group only) to assess cervical as well as overall sagittal balance. A cervical spine CT will be obtained on patients at 1 year who have an NDI score > 30 or whose plain films suggest instability.

7) A study coordinator will collect data at 30 days and at 1 year to document any complications or re-operations. Additionally, the study coordinator will assess whether the patient is having any swallowing complications following surgery.

8) Health resource utilization information (including out-of-pocket expenses) will be obtained using patient diaries along with copies of all medical bills and receipts at 1 month, 3 months, 6 months, and 12 months post-operatively for all of the patients. Participants also will be asked to keep track of days missed from work and days unable to perform usual activities, in addition to days missed from work for medical treatments or evaluations.

F. Data and Safety Monitoring Plan

- 1) All serious unexpected adverse events (e.g. death within 30 days of operation) will be reported to the IRB within 24 hours. Any appropriate funding agencies or regulatory agencies would be notified as well.
- 2) Any serious anticipated adverse event (e.g. wound infection, pulmonary embolus) will be reported to the IRB whenever their magnitude or frequency exceeds expectations.
- 3) All other adverse events (including loss of privacy, significant economic harm) will be reported to the IRB on an annual basis or at the time that re-approval is sought. Any adverse event judged unlikely or unrelated to the study will also be included in an annual report for the IRB.

G. Statistical Considerations

a. Specific data variables being collected for the study.

The data collection sheets will be submitted along with this protocol. There will be several data sheets as follows:

- 1) Screening/Baseline, 1 Month, 3 Months, 6 Months, and 1 Year Visit Checklist
- 2) Informed Consent Process
- 3) Inclusion/Exclusion Criteria
- 4) Baseline Demographics
- 5) Spine surgeon's data sheet

- 6) 30-day and 1 Year morbidity data sheet
- 7) 1 Month, 3 Months, 6 Months, 1 Year Return to Work Status
- 8) 3 Month Swallowing Evaluation

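### The as-treated return-to-work contrasts are tested at 0.025 by log-rank with no adjustment specified, although choice of dorsal procedure is not randomized, so they may be confounded

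*Combined protocol and SAP*

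**What the plan says.** The Analysis Plan for Return to Work (section II.G.c) has three sentences.

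- **Data:** "The return to work analysis will include all time periods up to 12 months (1, 3, 6, and 12 months"). The data-sheet list in II.G.a has the matching form, "1 Month, 3 Months, 6 Months, 1 Year Return to Work Status".
- **Method:** "Groups will be compared via Kaplan-Meier plots and log-rank tests".
- **As-treated groups:** the third sentence sets a level of 0.025 for each of two pairwise tests. The stated reason is "to account for 2 comparisons (DL vs DF and DL vs VF"). I read DL, DF and VF as dorsal laminoplasty, dorsal fusion and ventral fusion.

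Nothing is said about stratification, weighting, regression, sensitivity analysis, or which patients are at risk of returning to work.

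Section II.G.b makes work status a secondary endpoint: "as well as the observed complication rates, health service utilization, work status, and sagittal balance measurements". Section II.G.d shows what is randomized: "The following table describes the total sample size (2:3 ventral-dorsal randomization) required to detect a five point difference". Under II.A the dorsal arm covers both fusion and laminoplasty, and no random allocation between the two is described.

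**The concern.** Laminoplasty versus dorsal fusion is not a randomized contrast. Laminoplasty versus ventral fusion sets a selected part of the dorsal arm against the ventral group. Age, myelopathy severity and baseline function could plausibly influence both the procedure chosen and the time to resume work. An unstratified log-rank test takes no account of them.

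Two features make this more than a matter of presentation. The outcome is a named secondary endpoint. The contrasts also carry a formal significance level, so a p-value below 0.025 would invite reading as an effect of the procedure. Aim 2 asks whether loss of productivity differs among the same three procedures, so the result would be read alongside it.

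Two gaps add to this. Eligible ages run from 45 to 80, and the cost section treats retirees separately, yet the return-to-work plan does not define the risk set. It also does not say whether the as-treated groups include the 91 non-randomized patients. Under III.A, some of those were not randomized because the expert panel did not confirm equipoise.

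**Working it through.** **1. The plan's own figure.** 0.05 / 2 = 0.025, which reproduces. If the two tests were independent, the family-wise error would be 1 − (1 − 0.025)² = 0.0494. The level deals with multiplicity and has no bearing on confounding. The documents give no event count, hazard ratio or power for return to work, so there is no other figure to check.

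**2. Treatment of the same issue elsewhere in II.G.c.**

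| Analysis | Baseline adjustment | Status of as-treated comparisons |
|---|---|---|
| Primary PCS model | Baseline PCS and surgeon | Not applicable (intention to treat) |
| Year 2 outcomes | None; baseline said to be similar between groups | Exploratory; multiplicity not addressed |
| Cost GLM | Any imbalanced baseline characteristics | Not labelled |
| Return to work | None stated | Tested at 0.025; not labelled exploratory |

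Neither the exploratory label nor the similarity remark is carried over to return to work.

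**3. Imbalance visible in the documents.** The pilot table in II.G.d gives pre-operative PCS by procedure.

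- Laminoplasty (n = 28) 37.0, SD 10.9; dorsal fusion (n = 42) 35.0, SD 11.7. Pooled SD = √[(41 × 11.7² + 27 × 10.9²)/68] = 11.39. Difference 2.0 / 11.39 = 0.18 SD.
- Ventral (n = 45) 35.5, SD 10.3. Pooled SD with laminoplasty = √[(44 × 10.3² + 27 × 10.9²)/71] = 10.53. Difference 1.5 / 10.53 = 0.14 SD.

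Both gaps are modest. Age, occupation, pre-operative work status and mJOA are not tabulated by procedure.

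**4. Illustrative bias (assumed inputs).** Take a binary factor that halves the return-to-work rate (HR 0.5), with prevalence pa and pb in the two groups and no procedure effect. Approximate crude HR = (0.5·pa + 1 − pa)/(0.5·pb + 1 − pb).

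- 55% vs 45%: 0.725 / 0.775 = 0.935
- 60% vs 40%: 0.700 / 0.800 = 0.875
- 65% vs 35%: 0.675 / 0.825 = 0.818

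**5. What that does to the error rate.** I simulated the unadjusted log-rank test at nominal 0.025 under the step 4 splits, with no procedure effect. Assumptions: return-to-work rate 0.12 to 0.20 per month, visits at 1, 3, 6 and 12 months, 4,000 trials per setting. Group sizes use the pilot mix. The 82 analysable dorsal patients split as 82 × 28/70 ≈ 33 and 82 × 42/70 ≈ 49. All 159 + 91 = 250 patients give 250 × 28/115 ≈ 61 and 250 × 42/115 ≈ 91.

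| Split | 33 vs 49 | 61 vs 91 |
|---|---|---|
| 55/45 | about 0.03 | 0.03–0.04 |
| 60/40 | about 0.04 | 0.05–0.07 |
| 65/35 | 0.06–0.07 | 0.10–0.12 |

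A second set used a normally distributed confounder: log-HR 0.4 to 0.7 per SD, rate 0.12 per month, 50% to 100% of patients at risk, the same two sets of group sizes, 2,000 trials per setting. Error rates were 0.02–0.03 with no imbalance, 0.02–0.05 at the pilot gap of 0.18 SD, 0.03–0.09 at 0.3 SD and 0.04–0.25 at 0.5 SD.

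**The case against.** The strongest reply is that the randomized comparison is already there. The method sentence refers simply to groups, and the next one introduces the as-treated comparison as a case needing multiplicity control. The Year 2 plan just above compares both the randomized and the as-treated groups, and the primary analyses are by intention to treat. This stands: a reader might infer that return to work is compared only as treated, and the text does not support that. What is missing is a statement that the randomized comparison comes first.

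A reader might also infer that these contrasts are in fact confounded. The documents do not show that. The only pilot baseline variable given by procedure, PCS, differs by 0.18 SD or less, and the Year 2 section says baseline variables were similar between groups. That remark names no variables and concerns the Year 2 models, so it lessens the worry without settling it for work-related factors.

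Three further replies also stand. Log-rank tests can be stratified or weighted, so the fault is that neither is specified. The common visit schedule does not by itself bias the comparison. Lost productivity is also valued in the cost analysis, whose GLM adjusts for imbalance, so Aim 2 does not rest on these tests alone.

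None of these replies supplies an adjustment, or an exploratory label, for the two contrasts.

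**Conclusion.** The point holds in a limited form. Two non-randomized contrasts on a secondary endpoint are tested at a formal level with no adjustment specified, so they may be confounded. The randomized ventral-versus-dorsal comparison is unaffected.

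The size of any bias is unknown. Hazard ratios of about 0.82 to 0.94 under no effect are illustrations that rest on an assumed HR of 0.5 and assumed splits. With an imbalance like the pilot PCS gap, the inflation above 0.025 is small. It becomes material only with a marked imbalance in a strong predictor, more so if all 250 patients are pooled. It would be wrong to conclude that a significant laminoplasty result must be spurious. The supportable conclusion is that the plan, as written, would not separate selection from effect. The change is worth making and does not affect the primary endpoint.

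**What to change.** 1. Name the randomized ventral-versus-dorsal intention-to-treat comparison as the main return-to-work test.
2. For laminoplasty versus dorsal fusion and versus ventral fusion, base inference on a time-to-event model: Cox, or discrete-time given the four visits. Restrict it to patients working before surgery and adjust for a short prespecified list such as age, baseline mJOA and baseline PCS. Label these contrasts exploratory.
3. Keep the Kaplan-Meier plots and unadjusted log-rank tests for these contrasts as description.
4. State whether the 91 non-randomized patients are included.

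The cost is SAP wording and a little more analysis. Baseline PCS and mJOA are already collected; whether pre-operative work status is on the baseline form should be confirmed, since the form's fields are not shown. The downside is limited precision. The laminoplasty group may be small, and restricting to working patients shrinks it further, so full site terms (ten centers) and multi-level occupation terms should be avoided. Some confounding may therefore remain, which is why the exploratory label is needed as well as the adjustment.
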